10 EFFICACY ANALYSES

10.1 Incidence of BPD

BPD will be defined by the NICHD BPD estimator as a dichotomous (none-mild vs. moderate-severe) variable and as a categorical variable (none, mild, moderate, or severe) among survivors by modifying the NIH consensus definition of BPD to include infants transferred prior to 36 weeks and the need for oxygen at 36 weeks PMA (or discharge, if sooner than 36 weeks PMA). The severity of BPD is defined as follows:

1. **No BPD:** receiving > 21% supplemental oxygen (O_2) for ≤ 28 days and not at 36 weeks PMA
2. **Mild BPD:** receiving > 21% O_2 for ≥ 28 days but not at 36 weeks PMA
3. **Moderate BPD:** receiving > 21% O_2 for ≥ 28 days plus treatment with <30% O_2 at 36 weeks PMA

4. **Severe BPD:** receiving $> 21\% \text{ O}_2$ for ≥ 28 days plus $\geq 30\% \text{ O}_2$ and/or positive pressure at 36 weeks PMA

Note that the day in the definition above is postnatal day but not treatment day. Final assessment of BPD at 36 weeks PMA will be summarized by dose groups.

BPD will be evaluated through logistic regression models by whether the event occurred or did not occur at 36 weeks PMA assessment. Independent factors in the model will include gestational age, birth weight, dose groups. Confidence intervals will be calculated using the profile-likelihood.

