1.1 Study Synopsis

Protocol Title	Safety of Furosemide in Premature Infants at Risk of Bronchopulmonary Dysplasia (BPD)
Phase:	II
Protocol Version	Version 5.0, 7 April 2015
Product	Furosemide
Objective	Primary: Describe the safety of furosemide in premature infants at risk of BPD Secondary: Preliminary effectiveness and pharmacokinetics (PK) of furosemide
Study Design	Multi-center, randomized, placebo-controlled, dose escalating, double masked, safety study

Study Population	
Inclusion Criteria
 
 1. Documented informed consent from legal guardian, prior to study procedures 2. Receiving positive airway pressure (nasal continuous airway pressure, nasal intermittent positive pressure ventilation, or nasal cannula flow > 1LPM) or mechanical ventilation (high frequency or conventional) 3. < 29 weeks gestational age at birth 4. 7-28 days postnatal age at time of first study dose 
Exclusion Criteria
 
 1. Exposure to any diuretic ≤ 72 hours prior to first study dose 2. Previous enrollment and dosing in current study, “Safety of Furosemide in Premature Infants at Risk of Bronchopulmonary Dysplasia” 3. Hemodynamically significant patent ductus arteriosus, as determined by the investigator 4. Major congenital anomaly (e.g. congenital diaphragmatic hernia, congenital pulmonary adenomatoid malformation) 5. Meconium aspiration syndrome 6. Known allergy to any diuretic 7. Serum creatinine >1.7 mg/dl < 24 hours prior to randomization 8. BUN >50 mg/dl < 24 hours prior to randomization 9. Na <125 mmol/L < 24 hours prior to randomization 10. K ≤2.5 mmol/L < 24 hours prior to randomization 11. Ca ≤ 6 mg/dL < 24 hours prior to randomization 12. Indirect bilirubin >10 mg/dl < 24 hours prior to randomization 13. Any condition which would make the participant, in the opinion of the investigator, unsuitable for the study 																												
Number of Participants	120																												
Number of Sites	Approximately 30 sites																												
Duration of Participation:	Up to 35 days (28 days of study drug plus 7 days of safety monitoring). Information about hospitalization will be collected at 36 weeks post menstrual age and/or at discharge.																												

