 - c. NCPAP (or equivalent, see inclusion criteria in protocol synopsis table)
 - d. Cannula/Hood
 - e. None (room air with no support)

All respiratory assessments (including assessments outside the window) will be summarized by visit and dose groups.

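### The four BPD severity classes in SAP section 10.1 overlap and leave a gap, so for some infants the none-mild versus moderate-severe outcome is not defined

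*SAP*

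**What the plan says.** Section 10.1 of the SAP builds two variables among survivors: a four-level severity and a dichotomy that sets none and mild against moderate and severe. The classes use days on more than 21% oxygen and status at 36 weeks postmenstrual age (PMA):

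- No BPD: more than 21% oxygen "for ≤ 28 days and not at 36 weeks PMA".
- Mild: more than 21% oxygen "for ≥ 28 days but not at 36 weeks PMA".
- Moderate: at least 28 oxygen days "plus treatment with <30% O_2 at 36 weeks PMA".
- Severe: at least 28 oxygen days with 30% oxygen or more "and/or positive pressure at 36 weeks PMA".

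The lead sentence says that a published consensus definition is modified to cover transferred infants and "the need for oxygen at 36 weeks PMA (or discharge, if sooner than 36 weeks PMA". A note adds: "Note that the day in the definition above is postnatal day but not treatment day". The classes feed a summary by dose group and a logistic regression of whether the event occurred (table 14.2.1). The model sentence does not define the event. No order of precedence among the classes is given.

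**The concern.** A severity scale used as an outcome should place every assessed infant in exactly one class. This one does not, and two of the failures reach the dichotomy.

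(a) Mild is worded by oxygen only, while positive pressure alone is enough for Severe. An infant with at least 28 oxygen days who is on positive pressure in 21% oxygen at 36 weeks is a non-event by one line and an event by another.

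(b) Mild, Moderate and Severe all require at least 28 oxygen days, and No BPD requires that the infant is not above 21% oxygen at 36 weeks. An infant with fewer than 28 oxygen days who is above 21% at 36 weeks meets none of the four. Section 7 rules out imputation outside the PK analysis, so an infant left unclassed would drop out of the model unless someone supplies a rule.

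Two programmers following section 10.1 could report different BPD rates from the same data. If severity is recorded on a form and not derived (listing 16.2.8.6 is separate from the respiratory listing 16.2.8.5), the same ambiguity passes to whoever completes the form.

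**Working it through.** Section 10.1 states no numerical result to reproduce, so the check is to apply the four definitions as written.

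**Inputs, all from section 10.1:** oxygen days (fewer than 28, exactly 28, more than 28); oxygen at 36 weeks (21%, 22–29%, 30% or more); positive pressure at 36 weeks (no, yes). This gives 3 × 3 × 2 = 18 combinations. Moderate is taken to need more than 21% oxygen.

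| Oxygen days | Oxygen at 36 weeks | Positive pressure | Combinations | Classes met | Event if moderate-severe | Event if any BPD |
|---|---|---|---|---|---|---|
| <28 | 21% | either | 2 | No BPD | no | no |
| <28 | >21% | either | 4 | none | undetermined | undetermined |
| 28 | 21% | no | 1 | No BPD, Mild | no | undetermined |
| 28 | 21% | yes | 1 | No BPD, Mild, Severe | undetermined | undetermined |
| >28 | 21% | no | 1 | Mild | no | yes |
| >28 | 21% | yes | 1 | Mild, Severe | undetermined | yes |
| ≥28 | 22–29% | no | 2 | Moderate | yes | yes |
| ≥28 | 22–29% | yes | 2 | Moderate, Severe | yes | yes |
| ≥28 | ≥30% | either | 4 | Severe | yes | yes |

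- One class: 2 + 1 + 2 + 4 = 9.
- More than one class: 1 + 1 + 1 + 2 = 5.
- No class: 4.
- With moderate-severe as the event, 1 + 1 + 4 = 6 combinations have no determined value. They amount to two situations: overlap (a), counted at 28 days and above 28 days, and gap (b), subdivided by oxygen level and pressure.
- With any BPD as the event, overlap (a) above 28 days no longer matters, but the 28-day tie between No BPD and Mild then crosses the split.

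**Can these states occur?** Section 9.5 collects oxygen level and ventilation type as separate items at 36 weeks, one type being "NCPAP (or equivalent, see inclusion criteria in protocol synopsis table", so pressure in 21% oxygen can be recorded. Entry requires support, "Receiving positive airway pressure (nasal continuous airway pressure, nasal intermittent positive pressure ventilation, or nasal cannula flow > 1LPM" or mechanical ventilation, with no minimum oxygen level. For the latest eligible birth (28 weeks 6 days), 36 weeks falls at postnatal day 36 × 7 − (28 × 7 + 6) = 252 − 202 = 50. If the 28 days were read as status at postnatal day 28, an infant off oxygen that day and on it at day 50 or later would still be unclassed, and overlap (a) would remain.

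**Size.** The SAP gives no frequency. Assuming 1, 2 or 3 affected infants in a group of 30, the rate moves by 1/30 = 3.3, 2/30 = 6.7 or 3/30 = 10 points, and by more if the denominator is survivors only. For scale, the Wilson width is 2z/(1 + z²/n) × √(p(1 − p)/n + z²/(4n²)). With n = 30 and z = 1.96 this is 3.475 × √(0.00533 + 0.00107) = 0.28 at p = 0.2 and 3.475 × √(0.00700 + 0.00107) = 0.31 at p = 0.3, which agrees with SAP Table 2.

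**The case against.** The strongest reply is that a sensible reader can repair the text. The classes run from none to severe, and putting an infant on pressure in 21% oxygen into Mild would empty the pressure clause of Severe where it matters most for the dichotomy, so the highest class is the natural choice. The lead sentence on need for oxygen at 36 weeks points to moderate-severe for the gap infants. The two readings are compatible and together settle every combination for the dichotomy. That is fair, and it shows that the endpoint can be rescued. But neither rule is written, each alone leaves one defect open (the first leaves the gap, the second leaves overlap (a)), and the lead sentence does not say which of the four levels a gap infant takes.

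It is also fair that the form behind listing 16.2.8.6 may carry its own instructions, and that the entry criterion applies at postnatal day 7–28 and says nothing about how often pressure in 21% oxygen occurs at 36 weeks.

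A reader might also infer more than the SAP supports:

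- That Moderate, worded only as below 30%, takes in infants in room air. The phrase concerns treatment with oxygen, and the other lines define oxygen as above 21%, so that reading is strained and is not used here.
- That 6 of 18 combinations means a third of infants. Combinations are not infants, and exactly 28 days is a single value that takes up a third of the table.
- That the comparison between arms is biased. Whatever rule is chosen would apply to all groups, and nothing in the SAP suggests otherwise.

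**Conclusion.** The point holds, with limited stakes. As written, the four classes contradict each other for infants with at least 28 oxygen days on positive pressure in 21% oxygen at 36 weeks, and omit infants with fewer than 28 oxygen days who are above 21% at 36 weeks. Exactly 28 days (No BPD and Mild) and 22–29% oxygen with positive pressure (Moderate and Severe) are lesser overlaps that affect only the four-level summary, provided the modelled event is moderate-severe. That is the likelier reading given the stated dichotomy, but section 10.1 does not say so.

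What is at risk is each group's absolute BPD rate and the reproducibility of table 14.2.1. The 3.3 to 10 point shift rests on an assumed 1 to 3 infants per 30, and is small beside intervals 28 to 31 points wide. BPD is listed in section 2.2.3 among the other outcomes, and section 7 calls the analyses exploratory or descriptive. The change should be made because it is cheap and removes a choice that would otherwise be made after the data are seen. No main conclusion of the trial depends on it.

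**What to change.** Before database lock, reconcile section 10.1 with the source definition that it says it modifies, then:

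1. State that the most severe class met applies. This settles overlap (a) and the Moderate/Severe overlap.
2. Make the 28-day boundary exclusive between No BPD and Mild, worded to agree with step 1 and with the other classes.
3. Assign infants with fewer than 28 oxygen days who are above 21% oxygen at 36 weeks by one stated rule. Otherwise, report their number per dose group and run the logistic model twice, counting them first as events and then as non-events.
4. State that the modelled event is moderate-severe BPD, if that is intended.

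If severity is recorded on a form, check the recorded class against the same rules. With steps 1 and 2, 14 of the 18 combinations fall in one class, and step 3 covers the other 4.

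The cost is a few lines of SAP text, plus derivation code or a consistency check. No data item is added beyond those the current definition already uses. Section 9.5 lists oxygen level and ventilation type at 36 weeks but no count of oxygen days, so that count must come from a form not shown.

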7 GENERAL ISSUES FOR STATISTICAL ANALYSIS

Descriptive statistics such as number of observations, mean, median, standard deviation, standard error, minimum and maximum will be presented by dose groups for continuous variables (such as age, weight, etc.). The dose groups will include furosemide groups (by dose level and across all dose levels), placebo group and overall. Other descriptive statistics such as counts, proportions, and/or percentages will be presented by dose groups to summarize discrete variables (such as race, sex, etc.).

Missing data will not be imputed in the non-PK analysis of this study.

Patient profile graphs showing chronologically the dosing, PK sampling, laboratory results of interest, risk of BPD, and adverse events for each participant will be developed.

All confidence intervals and tests will use $\alpha=0.05$. Analyses in this study are exploratory or descriptive in nature. No adjustments for multiplicity between endpoints are planned. Analyses will be performed using SAS Software version 9.2 or later.

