10.2 Risk of BPD

The preliminary effectiveness analysis will be on the risk of BPD which is provided by BPD estimator. The risk of BPD is presented as a % and the dichotomized the outcome will be used in the analysis (none-mild vs. moderate-severe-death). The BPD outcome estimator uses the following information to provide individual risk of BPD:

1. Gestational age (weeks)
2. Birth weight (g)
3. Sex
4. Maternal Race/Ethnicity
5. Postnatal day
6. Ventilation type (on the postnatal day of interest)
7. F_iO_2 (%) (on the postnatal day of interest)

For example, a 25 week Hispanic female with birth weight of 689 g on postnatal day 14 on mechanical ventilation with a FiO_2 of 0.45 has risk of no BPD of 1.6%, mild 27.9%, moderate 28.9%, severe 30.5%, and death 11%. Thus, none-mild risk is 29.5% and moderate-severe-death risk is 70.5%.

The risk of BPD or death as defined by the NICHD Neonatal Research Network (NRN) BPD estimator will be evaluated at baseline, on days 7, 14, 21 and 28 of study drug, the postnatal days closest to these days will be used in the BPD estimator. The postnatal day will be re-grouped to fit the BPD estimator: day 0 and day 1 will be re-grouped as day 1, day 2 and day 3 as day 3, 4-7 days as day 7, 8-14 as day 14 and 15-21 as day 21. The BPD estimator includes infants up to 28 postnatal days; for infants older than that, the 28 day estimates will be used. The birth weight used in the BPD estimator is up to 1250g, for infants with birth weight greater than 1250g, 1250g will be used. The BPD estimator includes white, black, or Hispanic infants; infants with other race/ethnicity will be excluded from the estimation. Sensitivity analyses may be done by removing infants with birth weight greater than 1250g.

The change of risk of BPD (as a percentage) from baseline to the end of study (day 28 or LOCF) will be assessed using an analysis of covariance (ANCOVA) model, with percentage change from baseline as the dependent variable. Independent factors include baseline risk percentage and dose groups.

As an exploratory analysis, a longitudinal mixed effect model may be used to test the risk of BPD at baseline and days 7, 14, 21 and 28 (with no LOCF). This longitudinal analysis will use all available risk of BPD percentages at each time point. Fixed effects will include treatment groups, dose level and dosing days; random effects will include participant. Linear and nonlinear

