14.2 EFFICACY			
14.2.1	Safety	Analysis of BPD at 36 Weeks PMA Assessment	16.2.8.6
14.2.2	Safety	Analysis of Change of Risk of BPD from Baseline to End of Study	16.2.8.5
14.2.3	Safety	Longitudinal Analysis for Risk of BPD	16.2.8.5

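### Section 10.1 gives deaths before 36 weeks no valid place in the observed BPD model, and no analysis of observed BPD or death is planned beside it

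*SAP*

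**What the plan says.** **Definition and model.** SAP section 10.1 defines observed BPD in two ways: dichotomised (none-mild against moderate-severe) and "as a categorical variable (none, mild, moderate, or severe) among survivors". Neither has a level for death, and each grade depends on oxygen or pressure support at 36 weeks PMA, or at discharge if that is sooner. The model follows: "BPD will be evaluated through logistic regression models by whether the event occurred or did not occur at 36 weeks PMA assessment". Its terms are gestational age, birth weight and dose group, with profile-likelihood intervals. The sentence does not say which of the two variables supplies the event.

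**Missing data and population.** Section 7 says "Missing data will not be imputed in the non-PK analysis of this study". The matching table, 14.2.1 ("Analysis of BPD at 36 Weeks PMA Assessment"), is assigned to the Safety population, which section 6 defines as everyone randomized and dosed.

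**Where death does appear.** In section 10.2 the dichotomised outcome "will be used in the analysis (none-mild vs. moderate-severe-death"), but this is the estimator's predicted risk at baseline and study days 7, 14, 21 and 28, with last observation carried forward in the main analysis. Section 2.2.3 lists death as an outcome separate from BPD, and section 9.1 makes death by 36 weeks PMA a seriousness criterion. The three efficacy tables (14.2.1 to 14.2.3) cover BPD at 36 weeks, change in predicted risk, and longitudinal predicted risk. None covers observed BPD or death.

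**Status.** Section 7 adds: "Analyses in this study are exploratory or descriptive in nature".

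**The concern.** An infant who dies before 36 weeks PMA cannot be graded. The SAP does not say what the logistic model does with that infant, and the two handlings that its text allows both have a drawback.

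- **Dropped.** This is the natural reading of a definition confined to survivors with no imputation. The dose-group odds ratio then compares infants selected by a post-randomisation event. Gestational age and birth weight remove only the selection that they explain. Section 10.2 names ventilation type and inspired oxygen as further predictors, and neither is in the 10.1 model.
- **Kept as not having the event.** This is the reading that the Safety label on table 14.2.1 leaves open. A dose group with more deaths would then look as if it had less BPD.

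The predicted-risk analysis in 10.2 does not fill the gap. It stops at study day 28, and for an infant who has died, carrying the last value forward keeps a predicted probability and never scores the death. At stake is how a dose-group odds ratio with its interval is read. Section 1 allows for planned analyses to go into a study report, regulatory submissions or manuscripts.

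**Working it through.** The SAP gives no death rates by dose group, so the size cannot be derived from it. The figures below are illustrative and unadjusted.

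**Inputs.** The worked example in section 10.2 is one ventilated 25-week infant, who "has risk of no BPD of 1.6%, mild 27.9%, moderate 28.9%, severe 30.5%, and death 11" (per cent). It is not a trial average. The SAP continues: "Thus, none-mild risk is 29.5% and moderate-severe-death risk is 70.5" (per cent).

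**Check of the SAP's figures.** None-mild: 1.6 + 27.9 = 29.5, as stated. Moderate-severe: 28.9 + 30.5 = 59.4. With death: 59.4 + 11 = 70.4, against 70.5 stated. The five risks sum to 99.9, so this is rounding. Rescaled to 1: none-mild 0.2953, moderate-severe 0.5946, death 0.1101. Moderate-severe is 59.4/88.9 = 66.8% among survivors, and moderate-severe or death is 70.5%.

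**If deaths drop out.** Assume x more deaths in a furosemide group than on placebo.

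- (a) All extra deaths fall on would-be moderate-severe cases: survivor OR = (0.5946 − x)/0.5946.
- (b) 80% fall on them, against a proportional share of 66.8%: survivor OR = [(0.5946 − 0.8x)/(0.2953 − 0.2x)] ÷ [0.5946/0.2953].
- (c) Deaths are non-selective: both survivor categories shrink by the same factor, so the survivor OR is 1.00.

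In each case BPD-or-death is 1 minus the none-mild proportion.

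| x | (a) survivor OR | (a) BPD-or-death | (b) survivor OR | (b) BPD-or-death OR | (c) survivor OR | (c) BPD-or-death |
|---|---|---|---|---|---|---|
| 0.05 | 0.92 | 70.5% (OR 1.00) | 0.97 | 1.05 | 1.00 | 72.1% (OR 1.08) |
| 0.10 | 0.83 | 70.5% (OR 1.00) | 0.93 | 1.10 | 1.00 | 73.8% (OR 1.18) |
| 0.15 | 0.75 | 70.5% (OR 1.00) | 0.89 | 1.16 | 1.00 | 75.4% (OR 1.29) |

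In (b) the two odds ratios point in opposite directions. In (c) the survivor odds ratio correctly describes BPD among survivors; it simply does not show the worse combined outcome.

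**If deaths are counted as no event.** Take (c) with x = 0.10. Moderate-severe on drug is 0.5946 × 0.7899/0.8899 = 0.5278. OR = (0.5278/0.4722) ÷ (0.5946/0.4054) = 0.76, while the BPD-or-death OR is 1.18.

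**Direction reversed.** Hold BPD-or-death equal in both groups at C, with death rates d. Moderate-severe among survivors is (C − d)/(1 − d), so the survivor OR reduces to (C − d_drug)/(C − d_placebo). With C from 50% to 70.4%:

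- placebo deaths 11%, drug deaths 20%: 0.30/0.39 = 0.77 to 0.504/0.594 = 0.85;
- placebo deaths 11%, drug deaths 5%: 0.654/0.594 = 1.10 to 0.45/0.39 = 1.15;
- equal deaths: 1.00.

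**Precision.** With 30 infants on one dose and 30 on pooled placebo, the unadjusted Wald 95% interval for (a) at x = 0.15 uses expected survivor counts 13.3 and 8.9 on drug, 17.8 and 8.9 on placebo. The standard error of log OR is √(1/13.3 + 1/8.9 + 1/17.8 + 1/8.9) ≈ 0.60, giving 0.75 (0.23 to 2.41). Five percentage points of mortality is 0.05 × 30 = 1.5 infants.

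**The case against.** The model sentence itself does not mention survivors. That wording sits in the definition, next to the four-grade variable, and the table is labelled Safety. This stands: the survivor restriction is inferred, not stated. But the dichotomous variable has no death level either, so the alternative is that deaths count as no BPD, which is worse.

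A reader might infer that the planned model is biased in favour of furosemide. The document does not support that. It gives no death rates by group, and fewer deaths on drug would push the survivor odds ratio above 1. Case (a) is an extreme, the base rates come from one infant, and every shift shown is small beside its interval.

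A reader might also infer that the composite should replace the survivor model as the basis for every dose statement. It should not. In case (a), 5 to 15 points of excess mortality leave BPD-or-death unchanged, so the composite alone would hide them. And in case (c) the survivor result answers a different question without being wrong.

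Finally, the primary outcome is adverse events, observed BPD is an additional outcome, all analyses are exploratory or descriptive, and deaths by 36 weeks PMA enter the serious-event tables by dose group. All of this stands and limits the stakes. It does not supply an analysis of observed BPD or death, nor say how deaths enter the 10.1 model.

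**Conclusion.** The point holds as a gap in how section 10.1 treats death. As written, infants who die before 36 weeks PMA either leave the model or count as free of BPD, and no analysis of observed BPD or death is planned, although the secondary effectiveness measure combines the two as predicted risk. When death rates differ between dose groups, either handling can misstate the dose effect. The direction and size depend on death rates that the SAP does not give. Under the assumptions shown, the survivor odds ratio runs from 0.75 to 1.15 while BPD-or-death is equal between groups, and it can point the opposite way to the composite (0.93 against 1.10). With equal, similarly distributed deaths there is no distortion. The change is worth making before database lock, but no primary or confirmatory conclusion depends on it.

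**What to change.** In section 10.1 and table 14.2.1:

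1. Add a logistic model of observed moderate-severe BPD or death by 36 weeks PMA, in all randomized and dosed infants with known outcome, using the same covariates and profile-likelihood intervals.
2. State that deaths are not coded as no BPD.
3. Keep the planned BPD model, name its event (moderate-severe BPD) and label it as conditional on survival.
4. Show, by dose group, deaths, survivors without a 36-week (or earlier discharge) assessment, and the evaluable number.
5. Say that the composite, the survivor model and the death counts are to be interpreted together.

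First confirm from the protocol and case report forms that deaths up to 36 weeks PMA are captured. Section 9 ends safety assessment 7 days after the last dose. For a 25-week infant first dosed at postnatal day 7 to 28 and treated for 28 days, that is 25 + (1 to 4) + 4 + 1 = 31 to 34 weeks PMA. Sections 1.1, 2.2.3, 3.1 and 9.1 point to later capture without settling it.

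The cost is one more model and a few table rows. The composite mixes two outcomes of unequal gravity, which is why its components must stand beside it.
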